3. STUDY OVERVIEW

3.1 Study Design

This is a multi-center, randomized, double-blind, parallel-group, three-arm, placebo-controlled, therapeutic equivalence study with clinical endpoints. The study will compare the efficacy and safety of test product "Oxymetazoline hydrochloride Cream, 1%" (manufactured by Actavis Laboratories, Salt Lake City, UT) with that of an approved topical formulation RHOFADETM (Oxymetazoline hydrochloride Cream, 1%) marketed by Allergan, in healthy males and non-pregnant females diagnosed with moderate to severe persistent facial erythema of rosacea. Both the test and the reference formulations will also be compared to a placebo (vehicle) formulation to test for superiority.

Subjects with a confirmed diagnosis of moderate to severe persistent facial erythema of rosacea will be randomized to either Test Group (Oxymetazoline hydrochloride Cream, 1%); Reference Group (RHOFADETM, Oxymetazoline hydrochloride Cream, 1%); or Placebo Group (Vehicle Cream).

The study subjects will receive treatment for approximately 29 days from the Baseline visit to the End of Treatment (EoT) visit. There will be 4 study visits, 3 to the study site and 1 telephone follow-up:

- Screening
- Baseline (Day 1
- Telephone Follow-up (Day 14
- End of Treatment (Day 29

At screening a written Informed Consent Form (ICF) has to be signed by the subject and the eligibility criteria of the subject will be evaluated by clinical assessments.

. Subjects should sign ICF prior to start of any study procedures, complete washout, and return to the clinic to conduct the remainder of the screening procedures.

Study subject numbers will be assigned to study subjects sequentially in the order in which study subjects are enrolled into the study.

After the screening visit, each qualified subject will return to the clinic on Day 1 for confirmation of eligibility. Eligible subjects will be assigned to one of the three study treatment groups as per the computer-generated randomization schedule, and the assigned study medication will be dispensed by the study site staff. Since this is a double-blind study, neither the study team at the site nor the subjects will know the treatment the subject is assigned.

The subject will be instructed to apply a pea-size amount of the study treatment to cover the entire face (forehead, chin, nose, and each cheek [avoiding the eyes and lips]), once daily preferably, at the same time each day, up to and including the day before scheduled Visit 4 (Day 29 ± 2). . On Day 1 visit and Day 29±2 visit, the subject will apply the assigned medication at the clinic under the supervision of an Independent Dispenser (unblinded to the treatment the subject is receiving).). From Day 2 up to and including the day before scheduled Visit 4 (Day 29), the subject will be asked to self-apply the assigned medication once daily and complete the subject diary, handed over by the study site staff at Baseline visit. The subject will note the date and time of application of the study medication, any AE experienced, and any concomitant medication taken or changes from the existing ones, in the subject diary from Visit 2 (Day 1) to Visit 4 (Day 29). A phone call will be made around Day 14 to follow up for any change in concomitant medications, and check on compliance of study medication usage. 3.2 Sample Size

3.2 Sample Size

•	
·	
•	
	·

3.3 Randomization and Unblinding Procedures

Subjects will be randomly assigned in a treatment allocation ratio of 1:1:1 to receive the Test product or the Reference Product or the Placebo control, respectively. The randomization schedule for this study will be generated by a third-party vendor such that a non-study-assigned independent expert will allocate the subjects to one of the three treatment arms using a computer-generated automated process,

(respective to that site) will be retained at the study site following the completion of the study and should be available to regulatory authority inspectors at the time of site inspection to allow for verification of the treatment identity of each subject.

The Investigator, staff at the study site, study monitors, and data analysis/management personnel will be blinded to the treatment assigned to the subject. Only the Independent Dispenser will have access to the study medication, but their primary responsibilities will be limited to dispensing, collecting and observing and supervising the administration of the study medication by the subject on clinical visits. They will not participate in any activities.

In case of an emergency, if the details of the study drug are required for management of an emergency as per the opinion of Investigator, the Investigator can unblind the product that is received by the subject during the study.

At the conclusion of the study, after the database has been locked, each site will be sent the study randomization scheme (respective to their site) that should be retained with the study documents in the event of an FDA inspection along with evidence of when the randomization scheme was provided.

4. STUDY ENDPOINTS/OUTCOMES

Primary Efficacy Endpoint

The primary efficacy endpoint is the proportion of subjects with treatment success at all time-points 3, 6, 9, and 12 hours post application on Day 29. Treatment success is defined as having CEA score at least 2 grades lower than the baseline (Day 1 pre-dose) value.

Safety Endpoints

Safety endpoints include incidence of AEs.

5. HYPOTHESES TESTING

Hypothesis of Equivalence

A two-sided, continuity-corrected 90% confidence intervals on the Test-vs-Reference difference for the proportion of subjects with treatment success at all timepoints (3, 6, 9 and 12 hours post-application on Day 29) will be constructed. Therapeutic equivalence will be

established if the 90% confidence interval for the difference is contained within the interval [-0.20, +0.20] for the PP population.

Hypothesis of Superiority

The null hypotheses to be tested are that there is no difference in the proportions of subjects with treatment success at all time-points (3, 6, 9 and 12 hours post-application on Day 29). The evaluation of superiority will be conducted separately for the Test treatment versus the Placebo treatment and for the Reference treatment versus the Placebo treatment. The analysis will be conducted using two-sided, $\alpha = 0.05$, exact CMH test stratified by study site.

Superiority will be established if the success proportion for each active treatment is greater than, and statistically different from, that of the Placebo for the mITT population.

6. ANALYSIS SUBSETS

6.1 Safety Population

The safety population includes all randomized subjects who applied at least 1 dose of study medication in the study, as recorded in the subject diary.

The safety population will be the primary population for the safety analysis.

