5.6 Blinding

This is a double-blinded clinical end point bioequivalence study. Study medications will be provided in similar cartons to maintain study blinding.

If necessary, for the safety and proper treatment of the subjects, the Investigator can unblind the subject's treatment assignment to conduct appropriate follow-up care. Whenever possible, the Sponsor or medical monitor will be notified before unblinding the study medication. The date and signature of the person breaking the code as well as the reason for breaking the code and any associated AEs will be recorded in the subject's source documentation.

The Investigator, staff at the study site, study monitors, and data analysis/management personnel will be blinded to the treatment assigned to the subject. The study site will have at least one Independent Dispenser. The role of the unblinded Independent Dispenser will be to dispense and collect study medication to/from the subjects, maintain dispensing records, and ensure the study medication logs are complete and accurate. The Independent Dispenser will also be responsible for observing and supervising the administration of the study medication by the subject on clinic visits, Day 1 and Day 29. The subject will be requested not to discuss the appearance of the study medication with the Investigator or study staff outside of the Independent Dispenser. Independent dispenser should not participate in any activities other than the activities defined in this section. To ensure that information that could potentially bias handling of data is not disclosed, the packaging team will hold the randomization scheme until after database lock.

At the conclusion of the study, after the database has been locked, each site will be sent the study randomization scheme (respective to their site) that should be retained with the study documents in the event of an FDA inspection along with evidence of when the randomization scheme was provided.

Confidential Page 43 of 102

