The following is a list of all tests and procedures at Day 1

Pre-dose procedures

- Confirm subject's eligibility (check of inclusion / exclusion criteria) and randomize to treatment.
- Record vital signs (blood pressure, heart rate and oral body temperature).
- Investigator's assessment of the severity of facial erythema using the CEA scale at pre-dose.
- Subject's assessment of the severity of facial erythema using the SSA scale at pre-dose.
- Conduct urine pregnancy test (subjects of childbearing potential only).

 Review of Prior and concomitant medications and concurrent procedures
- Dispense the assigned study medication tube (to be done by Independent Dispenser).
- Hand over subject diary (to be done by study site staff).

Dosing

- Subjects will gently wash their face with a mild, non-medicated cleanser, rinse with warm water and pat dry.
- Subject should wash their hands with soap and water before and after applying treatment and to avoid contact of the study product with the eye or lips.
- Subject will apply a pea size amount of the assigned study medication to cover the entire face (forehead, chin, nose, and each cheek [avoiding the eyes and lips]), under the supervision of the amblinded Independent Dispenser. The Independent Dispenser will be a designated site staff; unblinded to the treatment and will not be involved in any other clinical assessment activities.
- Subject will note the date and time of application of the study medication in the subject diary.

Post-dose procedures

Confidential Page 50 of 102

• Subjects will be questioned about how they are feeling and if any AE experienced this will be recorded in the subject diary.

Version No.: 3.0;

- Subject will be advised to apply a pea-size amount of the assigned study medication to cover the entire face (forehead, chin, nose, and each cheek [avoiding the eyes and lips]), once daily preferably, at the same time each day, from Day 2 to Day 28 at home.
- Subject will be instructed to wash his/her hands before and after each application of study treatment and to avoid applying the study medication to the eyes, eyelids, lips, mouth, scalp, neck, ears, and any membrane of the inner nose, or open wounds.
- Subject will be instructed to refrain from using restricted/prohibited medications.

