7.6 Safety Assessment

Safety analyses will be performed on the safety population. No inferential analyses are planned.

The extent of exposure will be summarized using descriptive statistics. Subject exposure to the study medication will be characterized by study duration and treatment duration. Study duration will be defined as number of days from the date of first dosing to the date of EoT visit (Day 29); if the date of EoT visit is missing, the date of the last visit will be used (i.e., date of study visit minus date of first dosing plus 1). Treatment duration will be defined as number of days from the date of first dosing to last dose (i.e., date of last dose minus date of first dose plus 1). Study duration and treatment duration will be summarized using descriptive statistics by treatment group.

Adverse events will be coded using preferred terms and primary SOC from the current version of MedDRA. The AEs and SAEs are considered to be treatment-emergent if they have started or worsened after first application of any study drug up until the EoT visit. The incidence of TEAEs, treatment-emergent SAEs (TESAEs) and drug-related TEAEs and TESAEs will be summarized by treatment group in frequency tables. The maximum severity of a TEAE/TESAE experienced by a subject will be determined by the most severe rating recorded on the eCRF for the subject's given TEAE. TEAEs leading to study discontinuation and treatment-related TEAEs leading to study discontinuation will be summarized by preferred term within primary SOC. Individual subject listings will be generated for TEAEs and TESAEs, including subject age, sex, and race, sorted by primary SOC, preferred term, onset and stop date, onset day relative to the most recent dose, relationship, and severity.

Adverse events will also be collected both for the screening and baseline period (which will be referred to as pretreatment AEs). A listing of pretreatment AEs (including any SAEs) will be presented.

Incidence of concomitant medications will be summarized by treatment group. A listing by subject of all abnormal physical examination values will be provided. The vital signs (body temperature, systolic blood pressure, diastolic blood pressure and heart rate), will be reviewed by the Investigator or qualified delegate and will be summarized by descriptive statistics.

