6.2 Modified Intent to Treat Population (mITT Population)

The mITT population includes all randomized subjects who met all the inclusion and none of the exclusion criteria, have a CEA measurement at baseline (i.e. pre-dose on Day 1), applied at least one dose of study treatment, and have at least one post-baseline measurement for CEA or discontinue due to lack of treatment effect after completing 2 days of treatment.

This population will be used for analyses of superiority.

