7.7.5 Exposure to Product

The subjects will be instructed to use the diary to document all doses taken. Dosing information will be summarized on the eCRF.

Compliance with scheduled application of the study drug will be determined as [Actual number of applications] / [Planned number of applications] * 100%, where

- Actual number of applications will be taken from the eCRF ("Total number of doses applied" field in the "Investigational Product Use Compliance" form)
- Planned number of applications is 29.

Number of missed doses will be calculated as follows. The number of doses missed in the dosing period (between the first and the last study drug application) will be taken directly from the eCRF.

Duration of exposure will be calculated as Date of last use of study medication – Date of first use of study medication + 1. Duration of exposure will be summarized descriptively by treatment group.

Compliance and duration of exposure will be summarized for the Safety and mITT populations.

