11. APPENDICES

11.1 Study visit Schedule

	Visit 1a	Visit 1b	Visit 2	Visit 3	Visit 4
Procedures	Screening	Screening	Day 1 (Baseline)	Day 14 (Telephone follow-up) ^a	Day 29 (EoT)
Written informed consent	X				
Demographics (height, weight, body mass index (BMI), gender, race, ethnicity)	X				
Pregnancy test (Urine)	X	X	X		X
Medical and surgical history	X	X			
Prior and concomitant medications and concurrent procedures	X	X	X	X	X
Vital signs measurements (blood pressure, heart rate, body temperature)	X	X	Pre-dose and 12 hrs		Pre-dose and 12 hrs
Clinician Erythema Assessment (CEA)	X	X	Pre-dose, 3, 6, 9, and 12 hrs (± 30 minutes at each timepoint)		Pre-dose, 3, 6, 9, and 12 hrs (± 30 minutes at each timepoint)
Subject Self-Assessment (SSA) for rosacea facial redness	X	X	Pre-dose, 3, 6, 9, and 12 hrs (± 30 minutes at each timepoint)		Pre-dose, 3, 6, 9, and 12 hrs (± 30 minutes at each timepoint)
Physical examination	X				X
Review of Inclusion/Exclusion	X	X	Pre-dose (confirm eligibility)		
Randomization			X		
Dispense study medication tube			X		
Dosing (Days 1-29) ^b			X		X
Adverse event monitoring ^c	X	X	X	X	X
Subject diary review			X		X
Confinement in study clinic			≥12 hrs in clinic		≥12 hrs in clinic
Collection of study medication tube					X

^a 14 days after the first dose of study drug, a phone call will be made to follow-up on any changes in concomitant medications and check on compliance of study medication usage.

^b Subject will apply study medication once daily preferably at the same time each day from Day 2 to Day 28 at home, as instructed.

^c Including monitoring of application site dermatitis, application site pruritus, application site erythema, and application site pain, scaling or burning at Visit 2 and Visit 4.

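### Does tying the safety population to the subject diary leave dosed mITT subjects outside the safety tables?

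*SAP*

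**What the plan says.** SAP 6.1 sets the safety population as "all randomized subjects who applied at least 1 dose of study medication in the study, as recorded in the subject diary". It names no other evidence of dosing.

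SAP 6.2 asks that mITT subjects "applied at least one dose of study treatment, and have at least one post-baseline measurement for CEA", or stopped for lack of effect after 2 days of treatment. It names no source for the dose. SAP 6.3 draws the per-protocol (PP) population from the mITT, but no visible sentence places the mITT inside the safety population.

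The safety population matters because of Protocol 7.6: "Safety analyses will be performed on the safety population". For exposure, SAP 7.7.5 states that "Actual number of applications will be taken from the eCRF" and that "Compliance and duration of exposure will be summarized for the Safety and mITT populations".

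On conduct, Protocol 5.6 makes the Independent Dispenser "responsible for observing and supervising the administration of the study medication by the subject on clinic visits, Day 1 and Day 29". Under Dosing for the Day 1 visit, Protocol 6.2 says: "Subject will note the date and time of application of the study medication in the subject diary". The schedule in SAP 11.1 marks "Subject diary review" at Visit 2 and Visit 4.

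The population definitions of Protocol 7.4 and the text of SAP 7.5 are not in the public documents, so a rule there can be neither relied on nor ruled out. SAP 6.3 describes 7.5 as dealing with exclusion from the PP population.

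**The concern.** A safety population should contain everyone who was exposed. Making a patient-held diary the only named evidence of exposure looks fragile, because diaries get lost and early dropouts are the subjects least likely to return one. Some of them may have stopped because of an adverse event.

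Take an eligible subject with a pre-dose CEA who applies the Day 1 cream under observation, has a 3-hour CEA, then disappears with the diary. SAP 6.2 admits this subject to the mITT. SAP 6.1, read literally, may not admit the same subject to the safety population. The subject would then be missing from the numerator and denominator of the adverse event, application-site and vital-sign summaries. A subject who stops for lack of effect and keeps the diary is a second example. Protocol 4.4 keeps such a subject in the PP analysis as a failure, so even a PP subject could fall outside the safety population.

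The SAP also appears to use the diary in one place and the eCRF in another to establish the same fact, which would allow the two exposure tables to disagree.

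**Working it through.** The plan states no figure on this point. The check compares the definitions, follows the Day 1 procedures, and then sizes what is left.

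**1. Definitions side by side**

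- Safety = randomized, and at least one dose recorded in the diary.
- mITT = randomized, eligible, baseline CEA present, at least one dose applied (source not named), and either a post-baseline CEA or discontinuation for lack of effect after 2 days.

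The mITT lies inside Safety only if every mITT subject has at least one diary-recorded dose. The SAP does not say so, so the gap exists on paper. Baseline is Day 1 pre-dose, so any of the four Day 1 readings (3, 6, 9 and 12 hours) meets the CEA condition.

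**2. What happens on Day 1**

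- The diary is handed over before dosing (Protocol 6.2, pre-dose list).
- The subject applies the cream under the dispenser's supervision and enters the date and time in the diary (Protocol 6.2, Dosing).
- The subject stays in clinic for at least 12 hours (Protocol Table 6-1, SAP 11.1).
- A diary review is scheduled for the same visit (same tables).

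The first post-dose CEA comes 3 hours after an application that should already be in the diary. If the visit runs as written, a subject with any Day 1 post-dose CEA also has a diary-recorded dose. The same holds for the subject who stops after 2 days for lack of effect. SAP 6.1 asks that the dose was recorded; it does not ask that the diary came back at study end.

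**3. Is the eCRF a second source?**

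Protocol 5.7 determines compliance from the diary and then carries missed and extra applications to the CRF compliance page. SAP 7.7.5 has subjects document doses in the diary before dosing information is summarized on the eCRF. Protocol 9.4 lists the diary as a source document, and Protocol 9.2 says eCRF data come from source documents. For the dose count this is essentially one chain, diary to eCRF. A subject with no diary may have no dose count in either exposure table, so a disagreement between those tables is not shown.

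**4. How many subjects**

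Excluded per 100 dosed = 100 × (share lost after Day 1) × (share of those with no retrievable Day 1 entry).

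Neither share is in the documents. The values below are assumptions, 2–10% for the first and 0–20% for the second.

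| Lost after Day 1 | No retrievable entry | Excluded per 100 dosed |
|---|---|---|
| 10% | 20% | 100 × 0.10 × 0.20 = 2.0 |
| 5% | 5% | 100 × 0.05 × 0.05 = 0.25 |
| 2% | 5% | 100 × 0.02 × 0.05 = 0.1 |
| any | 0% | 0 |

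The top row multiplies two assumed maxima.

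**5. What such a subject would contribute**

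For a subject lost after Day 1, the summaries would lack at most one post-dose vital-sign set (12 hours), the Day 1 application-site evaluation, and any adverse event recorded by then. SAP 7.1 lists all data in general, and SAP 7.7.1 lists all adverse event information by subject. The data stay visible, and only table counts could move.

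**The case for a change.** The best case for a change is that it would be cheap: remove the diary phrase, accept any documented application, and state that the mITT is a subset of Safety. Evidence outside the diary does exist. The dispenser watches the dose and keeps dispensing records (Protocol 5.6), and Protocol 9.4 lists visit notes covering the start of study drug separately from the diary. A SAP is also meant to prevent case-by-case decisions after data are seen, and early dropouts are not a random subset.

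Part of this stands. The literal gap is real, and SAP 6.2 cannot be assumed to use the diary silently. A diary that goes home and never returns, with no note kept at site, remains possible despite the Day 1 review.

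It does not amount to a needed change. Exclusion requires either a failure of the Day 1 procedures or reading a recorded dose as a returned diary. Where that happens, a witnessed application documented in the visit notes points to one obvious answer, which is to include the subject. Protocol 5.6 keeps analysis staff blinded and withholds the randomization scheme until after database lock, so a decision taken before lock could not be steered by arm. Nor is it clear that the edit costs nothing: no visible text describes a database field for the witnessed application, so using it might mean going back to site notes.

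**Conclusion.** No change is called for. SAP 6.1 and 6.2 do not formally guarantee that the mITT lies inside the safety population, but the Day 1 procedures make that the expected result, and the remaining case is one that analysts would resolve sensibly. The number affected cannot be derived from the documents and may be zero. Under the assumed shares it runs from 0 to 2 per 100 dosed subjects, with 0.25 per 100 at 5% and 5%. No bias in adverse event rates can be stated. Equivalence is tested on PP and superiority on mITT, so neither uses the safety population.

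This conclusion assumes that the Day 1 diary entry and review take place as scheduled, and that a dose is treated as recorded when the entry was made, whether or not the diary is later returned. It does not depend on the unseen text of Protocol 7.4 or SAP 7.5. If the SAP is reopened for other reasons, widening the named evidence of dosing would be tidier drafting, but it offers no demonstrated gain.
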